## 6.2 DATA SHARING PLANS

### 6.2.1 Human Data Sharing Plan

#### What data will be shared?

I will share human data generated in this research for future research as follows:

Coded, linked data in an NIH-funded or approved public repository.

Coded, linked data in BTRIS (automatic for activities in the Clinical Center)

Identified or coded, linked data with approved outside collaborators under appropriate agreements.

#### How and where will the data be shared?

Data will be shared through:

An NIH-funded or approved public repository. Insert name or names: [ClinicalTrials.gov](https://ClinicalTrials.gov), [dbGaP](https://dbGaP).

BTRIS (automatic for activities in the Clinical Center)

Publication and/or public presentations.

#### When will the data be shared?

Before publication.

At the time of publication or shortly thereafter.

### 6.2.2 Genomic Data Sharing Plan

Unlinked genomic data will be deposited in public genomic databases such as dbGaP in compliance with the NIH Genomic Data Sharing Policy.

### **6.3 RESPONSE CRITERIA**

Response rate of pembrolizumab in patients with relapsed/refractory gray-zone lymphomas (GZL) and extranodal diffuse large B-cell lymphomas (DLBCL) will be assessed according to the International Working Group (IWG) response criteria and the International PCNSL workshop response criteria. In addition, we will also look at overall response rate according to the 5-point Lugano classification for interpreting FDG-PET scans.

When appropriate, for patients with disease involvement of the bone marrow at baseline, repeat assessment will be done to confirm response.

#### **6.3.1 Response Criteria for Lymphoma Lymphoma – GZL and DLBCL (not PCNSL)**

The following will be used to assess response in subjects with GZL and extranodal ABC, with the exception of PCNSL (see Section [6.3.2](#)).

##### **6.3.1.1 International Working Group (IWG) response criteria**

The International Working Group (IWG) response criteria will be used (Cheson et al.):

Response Category	Physical Examination	Lymph Nodes	Lymph Node Masses	Bone Marrow
CR	Normal	< 1 cm	< 1 cm	Normal
CRu	Normal	> 1 cm	> 75% decrease	Indeterminate
PR	Normal	Normal	Normal	Positive
	Normal	≥50% decrease	≥50% decrease	Irrelevant
	Decrease in liver/spleen	≥50% decrease	≥50% decrease	Irrelevant
Progression	Enlarging liver/spleen; new sites	New or increased > 50%	New or increased > 50%	Reappearance

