## **2 ELIGIBILITY ASSESSMENT AND ENROLLMENT**

### **2.1 ELIGIBILITY CRITERIA**

#### **2.1.1 Inclusion Criteria**

2.1.1.1 Patients must have a diagnosis of B-cell lymphoma confirmed by Laboratory of Pathology, NCI, that is relapsed from or refractory to prior therapy as follows:

- **Cohort 1:** B-cell lymphoma, unclassifiable, with features intermediate between diffuse large B-cell lymphoma and classical Hodgkin lymphoma (i.e., Gray-zone lymphoma or GZL)
- **Cohort 2:** Extranodal diffuse large B-cell lymphoma involving one or more of the specified extranodal sites (i.e., extranodal DLBCL). The following subtypes are included (they do not have to be confirmed as non-GCB subtype for study entry):
  - Primary CNS lymphoma (PCNSL)
  - Primary testicular lymphoma (PTL)
  - Primary breast lymphoma (PBL)
  - Primary cutaneous DLBCL, leg-type
  - Intravascular large B-cell lymphoma (IVBCL)
  - Diffuse large B-cell, NOS, activated B-cell type, involving 1 or more extranodal site

**NOTE:** For GZL, diagnosis will be in accordance with the 2016 World Health Organization classification of lymphoid malignancies. Patients diagnosed with other extranodal DLBCL subtypes or that are not otherwise specified (NOS) must be involved at least 1 extranodal site and must be considered non-GCB by local immunohistochemistry algorithms. Cases that are non-GCB by the Hans criteria are considered eligible as well as cases of DLBCL that are both CD10+ and MUM1+.

2.1.1.2 Evaluable disease by clinical exam (i.e., palpable lymphadenopathy, measurable skin lesions, etc.), laboratory assessment (i.e., lymphoma involvement of bone marrow or peripheral blood by morphology, cytology or flow cytometry), and/or imaging (measurable lymph nodes or masses on CT or MRI and/or evaluable FDG-avid lesions on PET)

2.1.1.3 Adequate tumor tissue (archival or fresh) must be available for correlative studies.  
**NOTE:** Tumor tissue may be from any previously collected tissue and adequacy is at the discretion of the Principal Investigator. If prior tissue is not available, patient must be willing to undergo baseline tumor biopsy.

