## 6.3.1.3 Lugano Classification of Response

Lugano classification of response criteria with PET (Cheson et al., 2014).

Response and Site	PET-CT Based Response	CT-Based Response
Complete	Complete metabolic response	Complete radiologic response All of the following:
Lymph nodes and extralymphatic sites	Score 1, 2, or 3* with or without a residual mass on 5PS†	
 
Target nodes/nodal masses must regress to <math>\leq 1.5</math> cm in LDi
 
No extralymphatic sites of disease
 
 
NOTE: It is recognized that in Waldeyer's ring or extranodal sites with high physiologic uptake or with activation within spleen or marrow (e.g., with chemotherapy or myeloid colony-stimulating factors), uptake may be greater than normal mediastinum and/or liver. In this circumstance, complete metabolic response may be inferred if uptake at sites of initial involvement is no greater than surrounding normal tissue even if the tissue has high physiologic uptake.

Nonmeasured lesions	Not applicable	Absent
Organ enlargement	Not applicable	Regress to normal
New lesions	None	None
Bone marrow	No evidence of FDG-avid disease in marrow	Normal by morphology; if indeterminate, IHC negative
Partial	Partial metabolic response	Partial remission All of the following:
Lymph nodes and extralymphatic sites	Score 4 or 5† with reduced uptake compared with baseline and residual mass(es) of any size At interim, these findings suggest responding disease. At end of treatment, these findings indicate residual disease.	
 
<math>\geq 50\%</math> decrease in SPD of up to 6 target measureable nodes and extranodal sites
 
 
When a lesion is too small to measure on CT, assign 5 mm x 5 mm as the default value; when no longer visible, 0 x 0 mm. For a node <math>>5</math> mm x 5 mm, but smaller than normal, use actual measurement for calculation.

Nonmeasured lesions	Not applicable	Absent/normal, regressed, but no increase
Organ enlargement	Not applicable	Spleen must have regressed by $>50\%$ in length beyond normal
New lesions	None	None

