### 6.3.7 Other

Evaluable for toxicity: All patients who receive at least 1 dose of pembrolizumab will be evaluable for toxicity.

**Evaluable for objective response:** Only those patients who have measurable or evaluable disease present at baseline, have received at least two doses of therapy, and have had their disease re-evaluated with radiographic imaging will be considered evaluable for response. These patients will have their response classified according to the definitions stated below. (NOTE: Patients who exhibit objective disease progression prior to the end of cycle 1 will also be considered evaluable.)

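### For non-PCNSL Cohort 2 patients with extranodal-only disease, the table printed for the primary ORR has no PR rule, and Section 9.3 can drop patients who progress without a scan

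*Combined protocol and SAP*

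**What the plan says.** Section 6.3 states that response "will be assessed according to the International Working Group (IWG) response criteria and the International PCNSL workshop response criteria". The Lugano classification is added as a further assessment, and Section 1.1.2 lists it as a secondary objective worded for FDG-PET.

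Section 6.3.1 opens with "The following will be used to assess response in subjects with GZL and extranodal ABC, with the exception of PCNSL". Under it come the IWG table (6.3.1.1), the five-point PET scale (6.3.1.2) and the Lugano table (6.3.1.3). PCNSL has its own table in 6.3.2.

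Section 6.3.1.1 says "The International Working Group (IWG) response criteria will be used". In the IWG table printed there:

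- The columns are physical examination, lymph nodes, lymph node masses and bone marrow.
- PR has three rows: everything normal except a positive marrow; a normal examination with at least 50% decrease in nodes and masses; and "Decrease in liver/spleen" with the same nodal decreases.
- Sites outside these columns are mentioned only under progression: "Enlarging liver/spleen; new sites".

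The CT-based PR rule in 6.3.1.3 uses a 50% or greater "decrease in SPD of up to 6 target measureable nodes and extranodal sites". Its footnote counts cutaneous and palpable lesions among non-nodal lesions.

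On who counts:

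- Section 2.1.1.2 admits "Evaluable disease by clinical exam (i.e., palpable lymphadenopathy, measurable skin lesions, etc", and also disease shown by blood or marrow.
- Section 6.3.7 requires two doses and that patients "have had their disease re-evaluated with radiographic imaging", but keeps those with objective progression before the end of cycle 1.
- Section 9.3 requires two doses plus a baseline and a follow-up scan, with no exception.

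**The concern.** Cohort 2 is defined by extranodal disease, and Section 9.2 plans 10 of its 20 patients as non-PCNSL. These are the patients graded by a table built around nodes. Read literally, it errs in both directions:

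- A skin lesion that shrinks by 60% but stays visible, in a patient with no nodal disease, fits no PR row. A genuine response is lost.
- A patient with intravascular disease, a normal examination, no enlarged nodes and a normal marrow satisfies every CR column before treatment. A patient with disease only in the marrow matches the first PR row before treatment.

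In practice someone would grade these patients by judgement. ORR is the only primary endpoint, and the trial is open-label, single-arm and single-institution, so that judgement should be fixed in advance. The evaluability rules add a smaller problem: patients removed for want of a scan would tend to be those who did badly, and their removal raises the ORR.

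**Working it through.** **1. The design figure.** Inputs from Section 9.2, Cohort 2: n=20, null rate 0.40, alternative 0.70, exact binomial test, one-sided 0.10.

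- P(X≥12 | 20, 0.40) = 0.0565 and P(X≥11 | 20, 0.40) = 0.1275, so 12 is the smallest count that meets 0.10.
- Power = P(X≥12 | 20, 0.70) = 0.8867. The plan states 88%, so the figure reproduces.

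**2. Weight of one patient.** One patient is 1/20 = 5 percentage points of ORR. Moving from 12 to 11 responders takes p from 0.057 to 0.128, across the 0.10 limit.

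**3. Effect of ungradable PRs.** Let m be the number of the 20 with non-PCNSL, extranodal-only disease, and s the share of their responses that are PR and cannot be recorded. The documents give neither; Section 9.2 caps m at 10 by plan. The responder count is then Bin(20−m, 0.70) + Bin(m, 0.70×(1−s)), and power is the probability that this sum is at least 12.

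| m | s=0.25 | s=0.50 | s=0.75 |
|---|---|---|---|
| 2 | 85.1% | 81.1% | 76.8% |
| 5 | 78.4% | 64.7% | 48.2% |
| 10 | 64.2% | 31.7% | 7.0% |

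At s=0.50 the expected recorded ORR is (18×0.70 + 2×0.35)/20 = 66.5% for m=2, (15×0.70 + 5×0.35)/20 = 61.3% for m=5, and (10×0.70 + 10×0.35)/20 = 52.5% for m=10, against a true 70%.

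The loss must be confined to patients whom this table grades. A 10% loss spread over all 20 (rate 0.63) gives power of 70.0%, but that includes PCNSL patients, to whom the table does not apply. The same 10% loss in the 10 non-PCNSL patients alone gives 80.6%, and in 5 extranodal-only patients 85.0%.

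**4. The two evaluability rules side by side.**

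| Patient | 6.3.7 | 9.3 |
|---|---|---|
| Objective progression in cycle 1, one dose | Evaluable | Not evaluable (fewer than 2 doses) |
| Two doses, progression on examination in cycle 2, never re-scanned | Not evaluable | Not evaluable |
| Skin-only disease, CT at baseline and after cycle 2 | Evaluable | Evaluable |

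Section 3.4.3 puts the first on-treatment scan after cycle 2, so the first two rows can occur. The third shows that examination-only disease is not excluded as such.

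**The case against.** Several points on the other side are sound and limit the concern.

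- A reader might infer that extranodal disease in Cohort 2 as a whole cannot be graded PR. It can: PCNSL is half the planned cohort and has its own PR rows in 6.3.2. Patients with concurrent nodal disease can reach the IWG rows, and the eligible category of ABC-type DLBCL NOS with an extranodal site does not exclude nodal disease. So 10 is a ceiling for m, not an estimate.
- A reader might infer that the scan requirement itself blocks a PR. It does not. CT is scheduled for everyone, the calendar notes let imaging be adapted to known sites, and imaging is also due at the end of treatment (3.6.3). What remains is the patient who progresses and is never re-scanned.
- The missing SD row cannot change the ORR, because SD is a non-response.
- The printed table may abbreviate a fuller published source, which was not available here. However, the protocol prints the table as its rule and does not say that the source overrides it.
- The opening sentence of 6.3.1 covers the Lugano table too, and nothing expressly confines the CT-based column to the secondary endpoint. That is the best defence. It stops short because Sections 1.1.1 and 6.3 tie the primary ORR to IWG, present Lugano as an addition, and never say which table governs when IWG has no applicable row.

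**Conclusion.** The concern holds in a narrow form. For non-PCNSL Cohort 2 patients with extranodal-only disease, the table printed for the primary ORR contains no PR rule, its nodal CR columns are already met at baseline when there is no nodal disease, and the printed rule that would serve is not assigned to the primary endpoint. Separately, 6.3.7 and 9.3 define evaluability differently, and a patient who progresses without a scan can leave the denominator.

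The size depends on m and s, which the documents do not give. With half of responses ungradable, power is 81% at m=2, 65% at m=5 and 32% at m=10. These figures assume a true rate of 0.70 in every subtype and 20 evaluable patients, and they treat ungradable PRs as non-responses. They leave out the opposite error, a CR or PR matched at baseline, which would inflate the ORR. At the cut-off a single patient is enough. The change should be made; the design figures themselves are correct.

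**What to change.** 1. In 6.3.1, state that for non-PCNSL patients with measurable extranodal lesions and no measurable nodal disease, the primary ORR uses the CT-based column of 6.3.1.3 as a whole, including measured cutaneous or palpable lesions as in its footnote. Applying the whole column avoids mixing size rules within one patient (nodal CR is below 1 cm in the IWG table and at most 1.5 cm in the CT-based column).
2. In the same place, state that disease seen only in blood, marrow or vessels is graded by the test that showed it at baseline. A sum of lesion products cannot grade such disease, and the CT-based column marks marrow as not applicable for PR.
3. Use one evaluability definition in 6.3.7 and 9.3: re-evaluated by the method used at baseline (imaging, examination, marrow or blood). In both sections, count patients who progress before the first scan as evaluable non-responders.
4. Date the change before the final analysis and also report the ORR under the current wording. Section 11.2 records the decision to close accrual early, and under Section 8.1.5 the investigator monitors unblinded efficacy data, so an undisclosed late change would be open to criticism.

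The cost is protocol wording and re-grading a limited number of patients from existing records. The downsides are one more criterion to cite for the primary endpoint, a possibly slightly lower ORR from the wider denominator, and a late change that must be disclosed.

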##### **6.3.1.2 The Five-Point Scale (5-PS) Deauville criteria**

The five-point scale (5-PS) has been validated for use at interim staging and at the end of treatment and was adopted as the preferred reporting method at the First International Workshop on PET in Lymphoma in Deauville, France (i.e., Deauville criteria), and in several international trials.

The 5-PS scores the most intense uptake in a site of initial disease:

1. if present, as follows: no uptake or no residual uptake (when used at interim)
2. slight uptake, but below blood pool (mediastinum)
3. uptake above mediastinal, but below or equal to uptake in the liver
4. uptake slightly to moderately higher than liver
5. markedly increased uptake or any new lesion (on response evaluation)

## 6.3.1.3 Lugano Classification of Response

Lugano classification of response criteria with PET (Cheson et al., 2014).

Response and Site	PET-CT Based Response	CT-Based Response
Complete	Complete metabolic response	Complete radiologic response All of the following:
Lymph nodes and extralymphatic sites	Score 1, 2, or 3* with or without a residual mass on 5PS†	
 
Target nodes/nodal masses must regress to <math>\leq 1.5</math> cm in LDi
 
No extralymphatic sites of disease
 
 
NOTE: It is recognized that in Waldeyer's ring or extranodal sites with high physiologic uptake or with activation within spleen or marrow (e.g., with chemotherapy or myeloid colony-stimulating factors), uptake may be greater than normal mediastinum and/or liver. In this circumstance, complete metabolic response may be inferred if uptake at sites of initial involvement is no greater than surrounding normal tissue even if the tissue has high physiologic uptake.

Nonmeasured lesions	Not applicable	Absent
Organ enlargement	Not applicable	Regress to normal
New lesions	None	None
Bone marrow	No evidence of FDG-avid disease in marrow	Normal by morphology; if indeterminate, IHC negative
Partial	Partial metabolic response	Partial remission All of the following:
Lymph nodes and extralymphatic sites	Score 4 or 5† with reduced uptake compared with baseline and residual mass(es) of any size At interim, these findings suggest responding disease. At end of treatment, these findings indicate residual disease.	
 
<math>\geq 50\%</math> decrease in SPD of up to 6 target measureable nodes and extranodal sites
 
 
When a lesion is too small to measure on CT, assign 5 mm x 5 mm as the default value; when no longer visible, 0 x 0 mm. For a node <math>>5</math> mm x 5 mm, but smaller than normal, use actual measurement for calculation.

Nonmeasured lesions	Not applicable	Absent/normal, regressed, but no increase
Organ enlargement	Not applicable	Spleen must have regressed by $>50\%$ in length beyond normal
New lesions	None	None
Bone marrow	Residual uptake higher than uptake in normal marrow but reduced compared with baseline (diffuse uptake compatible with reactive changes from chemotherapy allowed). If there are persistent focal changes in the marrow in the context of a nodal response, consideration should be given to further evaluation with MRI or biopsy or an interval scan.	Not applicable
No response or stable disease	No metabolic response	Stable disease
Target nodes/nodal masses, extranodal lesions	Score 4 or 5 with no significant change in FDG uptake from baseline at interim or end of treatment	$<50\%$ decrease from baseline in SPD of up to 6 dominant, measurable nodes and extranodal sites; no criteria for progressive disease are met
Nonmeasured lesions	Not applicable	No increase consistent with progression
Organ enlargement	Not applicable	No increase consistent with progression
New lesions	None	None
Bone marrow	No change from baseline	Not applicable

Response and Site	PET-CT Based Response	CT-Based Response
Progressive disease	Progressive metabolic disease	Progressive disease Requires at least 1 of the following:
Individual target nodes/nodal masses	Score 4 or 5 with an increase in intensity of uptake from baseline; and/or	An individual node/lesion must be abnormal with: 
 
• LDi <math>>1.5</math> cm, and
 
• Increase by <math>\geq 50\%</math> from PPD nadir, and
 
• An increase in LDi or SDi from nadir:               
 
○ 0.5 cm for lesions <math>\leq 2</math> cm
 
○ 1.0 cm for lesions <math>>2</math> cm
 
 
 

Extranodal lesions	New FDG-avid foci consistent with lymphoma at interim or end of treatment assessment	
 
• In the setting of splenomegaly, the splenic length must increase by <math>>50\%</math> of the extent of its prior increase beyond baseline (e.g., a 15-cm spleen must increase to <math>>16</math> cm). If no prior splenomegaly, must increase by at least 2 cm from baseline.
 
• New or recurrent splenomegaly
 

Nonmeasured lesions	None	New or clear progression of preexisting nonmeasured lesions
New lesions	New FDG-avid foci consistent with lymphoma rather than another etiology (e.g., infection, inflammation). If uncertain regarding etiology of new lesions, biopsy or interval scan may be considered.	
 
• Regrowth of previously resolved lesions
 
• A new node <math>>1.5</math> cm in any axis
 
• A new extranodal site <math>>1.0</math> cm in any axis; if <math><1.0</math> cm in any axis, its presence must be unequivocal and must be attributable to lymphoma
 
• Assessable disease of any size unequivocally attributable to lymphoma
 

Bone marrow	New or recurrent FDG-avid foci	New or recurrent involvement

Abbreviations: 5PS, 5-point scale; CT computed tomography; FDG, fluorodeoxyglucose; IHC, immunohistochemistry; LDi, longest transverse diameter of a lesion; MRI, magnetic resonance imaging; PET, positron emission tomography; PPD, cross product of the LDi and perpendicular diameter; SDi, shortest axis perpendicular to the LDi; SPD, sum of the product of the perpendicular diameters for multiple lesions.

\*A score of 3 in many patients indicates a good prognosis with standard treatment, especially if at the time of an interim scan. However, in trials involving PET where de-escalation is investigated, it may be preferable to consider a score of 3 as inadequate response (to avoid under treatment). Measured dominant lesions: Up to 6 of the largest dominant nodes, nodal masses, and extranodal lesions selected to be clearly measurable in 2 diameters. Nodes should preferably be from disparate regions of the body and should include, where applicable, mediastinal and retroperitoneal areas. Non-nodal lesions include those in solid organs (eg, liver spleen, kidneys, and lungs), GI involvement, cutaneous lesions, or those noted on palpation. Nonmeasured lesions: Any disease not selected as measured, dominant disease and truly assessable disease should be considered not measured. These sites include any nodes, nodal masses, and extranodal sites not selected as dominant or measurable or that do not meet the requirements for measurability but are still considered abnormal, as well as truly assessable disease, which is any site of suspected disease that would be difficult to follow quantitatively with measurement, including pleural effusions, ascites, bone lesions, leptomeningeal disease, abdominal masses, and other lesions that cannot be confirmed and followed by imaging. In Waldeyer's ring or in extranodal sites (eg, GI tract, liver, bone marrow), FDG uptake may be greater than in the mediastinum with complete metabolic response, but should be no higher than surrounding normal physiologic uptake (eg, with marrow activation as a result of chemotherapy of myeloid growth factors).

†PET 5PS: 1, no uptake above background; 2, uptake  $\leq$  mediastinum; 3, uptake  $>$  mediastinum but  $\leq$  liver; 4, uptake moderately  $>$  liver; 5, uptake markedly higher than liver and/or new lesions; X, new areas of uptake unlikely to be related to lymphoma.

